4.2.1.2 Minor Protocol Deviations

Minor deviations will include, but are not limited to, the deviations presented in [Table 2](#).

Table 2 - Definition of Minor Protocol Deviation Categories

Sub-Category	Description
Procedural violation	Violation of any study procedures not affecting safety or data evaluability
Time deviation (Plasma nicotine PK sample)	Assessments not taken at the correct time or within the allowed time window or date/time is missing (see Section 4.2.1.3)
Time deviation (other assessment)	Assessments not taken at the correct time or within the allowed time window or date/time is missing (see Section 4.2.1.3)
Assessment missing (Plasma nicotine PK sample)	Assessment is missing
Assessment missing (other assessment)	Assessment is missing
Randomization sequence	Subject randomized not according to the sequence of the subject numbers assigned during the screening visit

4.2.1.3 Assessment Time Points and Assessment Time Windows**Table 3 – Definition of Collection Time Points and Assessment Time Windows**

Assessment	Nominal Time point(s) (relative to T_0)	Time Window
Plasma nicotine PK samples	5 minutes prior to T_0	\pm 1 minute
	1 minute after T_0	+ 30 seconds
	2 minutes after T_0	+ 1 minute
	4 minutes after T_0	+ 1 minute
	6 minutes after T_0	+ 1 minute
	8 minutes after T_0	+ 1 minute
	10 minutes after T_0	+ 1 minute
	12 minutes after T_0	+ 1 minutes
	15 minutes after T_0	\pm 2 minutes
	30 minutes after T_0	\pm 2 minutes
	1 hour after T_0	\pm 5 minutes
	2 hours after T_0	\pm 5 minutes
	4 hours after T_0	\pm 5 minutes
	10 hours after T_0	\pm 5 minutes
	24 hours after T_0	\pm 10 minutes
ABOUT-Product experience	On Days 1, 2, and 3	Within 60 to 120 minutes after T_0
VAS craving and liking assessment	15 minutes prior to T_0 (for craving only)	Within 15 minutes
	4 minutes after T_0	\pm 1 minute
	10 minutes after T_0	\pm 1 minute

Philip Morris Products S.A.
 P4M3 Gen 2.0, P4-PK-04-US
 [REDACTED] Statistical Analysis Plan Number CA34617

Assessment	Nominal Time point(s) (relative to T_0)	Time Window
	15 minutes after T_0	± 1 minute
	30 minutes after T_0	± 2 minutes
	1 hour after T_0	± 5 minutes
	2 hours after T_0	± 5 minutes
	4 hours after T_0	± 5 minutes
	10 hours after T_0	± 5 minutes
Blood samples for λ_z	T1z after 8 hours	± 5 minutes
	T2z after 12 hours	± 5 minutes
	T3z after 16 hours	± 10 minutes
	T4z after 20 hours	± 10 minutes
ECG	Screening	Not applicable
	Day -1	Not applicable
	Days 1, 2, and 3	60 minutes ± 10 minutes after T_0
	Day 4	60 to 120 minutes after T_0
	Early Termination	Not applicable
Weight of P4M3 Gen 2.0 Cartridges	Days 1, 2, and 3	Before T_0 Within 120 min after T_0
Vital signs	Screening	Not applicable
	Day -1	Not applicable
	Days 1, 2, and 3	Before T_0
	Day 4	Not applicable
	Early Termination	Not applicable

4.2.2 Data Summarization

The number and percent of subjects with protocol deviations, and the number of protocol deviations, will be summarized. Summaries will be broken down by main deviation category (major/minor), sub-categories, and evaluability impact. Subjects will be counted once per deviation category, and can be counted for more than one deviation category.

4.3 Preliminary Data and Interim Analysis

There will be no interim analysis of this study data.

Philip Morris Products S.A.
 P4M3 Gen 2.0, P4-PK-04-US
 [REDACTED] Statistical Analysis Plan Number CA34617

5. PRODUCT DESCRIPTIONS

5.1 Test Product

P4M3 Gen 2.0 is an ENDS or electronic cigarette (e-cigarette), which produces an aerosol through vaporization of an e-liquid. P4M3 Gen 2.0 is composed of a Battery unit containing all the control electronics with the rechargeable battery and a disposable Cartridge containing the e-liquid and the heating element. The Battery unit comprises several functions. The device provides electrical power when required, which is activated by puff detection. The device has a “dry mesh detection” function to prevent overheating when the liquid on heater is not sufficient.

The Battery unit is charged via a USB port. The Battery unit also features a tactile function that will operate when the unit is turned on and off and when a puff is taken.

The Battery unit is controlled through a single multi-function button used for switching on and off and allowing the modification of both the haptic (vibration) and the power level. The Cartridge consists of a reservoir for storing the e-liquid, which also acts as the mouthpiece and includes the air flow channels to carry the aerosol from the heater to the user. The Cartridge contains the e-liquid, the mesh heater sub-assembly and the porous materials for liquid retention and transport from the reservoir to the heater. The Cartridge is disposed of when the e-liquid in the reservoir is depleted.

The P4M3 Gen 2.0 e-liquid formulations are composed of propylene glycol (PG), vegetable glycerin (VG), water, tobacco-derived nicotine, lactic acid, benzoic acid and could differ in flavors and nicotine concentrations. The following P4M3 Gen 2.0 e-liquid formulations (variants) will be investigated in this study ([Table 5.1](#)).

Table 5.1 P4M3 Gen 2.0 variants

Name	Name in the study	Nicotine concentration	e-liquid flavor
P4M3 Gen 2.0 Classic Auburn	CA35	3.5 %	Tobacco
P4M3 Gen 2.0 Classic Menthol	CM35	3.5 %	Menthol

5.2 Reference Product

Subject's own cigarettes (Cigarettes) will be used as a comparator.

Subjects' preferred brand of commercially available, regular or mentholated cigarettes will not be provided by the Sponsor.

All eligible subjects will be asked to purchase their usual brand of cigarettes prior to Admission (Day -1). Every subject needs to bring his/her pack of unopened, single-brand cigarettes.

6. PHARMACOKINETICS

6.1 Collection Schedule for Plasma Nicotine

Collection schedule is described in [Table 6.1](#).

Table 6.1 Plasma Nicotine Samples Collection Schedule

Day 1 (15 blood samples)	Prior to the start of product use (T0) 5 minutes \pm 1 minute (T-1). In relation to T0 from Day 1: T1 after 1 minute \pm 30 seconds, T2 after 2 minutes \pm 1 minute, T3 after 4 minutes \pm 1 minute, T4 after 6 minutes \pm 1 minute, T5 after 8 minutes \pm 1 minute, T6 after 10 minutes \pm 1 minutes, T7 after 12 minutes \pm 1 minute, T8 after 15 minutes \pm 2 minutes, T9 after 30 minutes \pm 2 minutes, T10 after 1 hour \pm 5 minute, T11 after 2 hours \pm 5 minutes, T12 after 4 hours \pm 5 minutes, T13 after 10 hours \pm 5 minutes and T14 after 24 hours \pm 10 minutes (Days 1, 2). The sample T14 on Day 1 will also be used to determine the nicotine baseline concentration prior to T0 on Day 2.
Day 2 (14 blood samples)	Same time points as on Day 1, except time point T1. The sample T14 after T0 on Day 1 will also be used to determine the nicotine baseline concentration prior to T0 on Day 2 and similarly, T14 after T0 on Day 2 for nicotine baseline concentration prior to T0 on Day 3.
Day 3 (13 blood samples)	Same time points as on Day 2, except no sample T14 after T0 on Day 3.
Day 2 (4 blood samples)	Samples for determination of the terminal elimination half-life (t _{1/2z}). In relation to T0 from Day 2: T1z after 8 hours \pm 5 minutes, T2z after 12 hours \pm 5 minutes, T3z after 16 hours \pm 10 minutes and T4z after 20 hours \pm 10 minutes.

6.2 Plasma Nicotine Concentrations

Analytical Laboratory

Samples will be analyzed for nicotine in plasma using a validated liquid chromatography coupled to tandem mass spectrometry (LC-MS/MS) detection analytical method with the appropriate quality controls in accordance with the Food and Drug Administration (FDA) Guidance for Industry: Bioanalytical Method Validation (May, 2001) and in accordance with FDA Good Laboratory Practice regulations (Title 21 CFR Part 58) at [REDACTED] Bioanalytical Services Lincoln, Nebraska.

In general, values below the lower limit of quantification (LLOQ) will be imputed using 0.5 x lower limit of quantification. For values above the upper limit of quantification (ULOQ), the ULOQ will be used for calculation and reporting in summary tables.

Philip Morris Products S.A.
P4M3 Gen 2.0, P4-PK-04-US

██████████ Statistical Analysis Plan Number CA34617

Plasma concentrations as determined at the collection times described in [Section 6.1](#) will be used for the calculation of the plasma nicotine PK parameters.

6.3 Plasma Nicotine Pharmacokinetic Parameters

Nicotine PK endpoints will be derived from the background-corrected plasma nicotine concentrations. Nicotine PK parameters will be derived from background-corrected plasma nicotine concentration versus time data using a non-compartmental analysis (NCA) technique using appropriate and validated PK software (e.g., Phoenix WinNonlin version 7.0 or higher).

For nicotine concentrations below the LLOQ (BLQ) for the calculation of descriptive statistics of observed plasma nicotine concentrations:

- BLQ values before T0 will be imputed by LLOQ/2.
- BLQ values after the last quantifiable value are not included in the analysis (e.g., for the calculation of AUC).
- Any BLQ value (after T0 and before the last quantifiable value) would need to be queried* and, if confirmed, it will be imputed by LLOQ/2.

*The query will be triggered at the latest by █████ data QC, and █████ will query the bioanalytical laboratory. The information on the value queried and a summarized response from the bioanalytical laboratory will be part of the SDTM data (e.g. in the CO domain).

The number and percent of values below LLOQ or above ULOQ will be presented in each summary table.

To minimize the carry-over effect in the nicotine plasma PK parameters due to limited washout periods, the correction for background-concentration (baseline nicotine level obtained pre-use) will be applied to the concentration data. This correction will be implemented by calculating the nicotine exposure parameters using background-corrected concentration values as described below.

The nicotine terminal elimination rate constant λ_z (and $t_{1/2z}$) will be estimated from the Day 2 PK samples listed in [Section 6.1](#) by using a linear regression on the log-transformed plasma nicotine concentration data. The regression analysis should contain data from at least 3 different time points in the terminal phase (including the last quantifiable concentration but excluding the concentration at T_{max}), consistent with the assessment of a straight line on the log-transformed scale. The nicotine plasma background-corrected PK parameters will be derived by performing the non-compartmental analysis (NCA) on the background corrected concentrations.

For the purposes of background-correction of the plasma concentrations post-baseline the following formula will be applied: $cC_t = C_t - C_0 \cdot * e^{-\lambda_z \cdot t'}$. Where, cC_t is the corrected concentration at each time point, C_t is the observed concentration at each time point, C_0 is the pre-use baseline concentration, λ_z is the Day 2 terminal elimination rate constant, t' is the actual time since start of product use, and t' is the actual time since the time of the pre-use baseline sample.

Philip Morris Products S.A.
P4M3 Gen 2.0, P4-PK-04-US

██████████ Statistical Analysis Plan Number CA34617

In particular, the following PK parameters will be derived from background-corrected nicotine levels following 6 minutes *ad libitum* use:

C_{\max}	Maximum background-corrected plasma concentration. C_{\max} will be reported as long as there is at least one quantifiable concentration post T_0 .
T_{\max}	Time to maximum background-corrected plasma nicotine concentration C_{\max} .
$AUC_{0-2\text{min}}$	Area under the background-corrected plasma concentration-time curve from start of product use (T_0) to 2 minutes.
$AUC_{0-4\text{min}}$	Area under the background-corrected concentration-time curve from T_0 to 4 minutes.
$AUC_{0-T_{\max}}$	Area under the background-corrected plasma nicotine concentration-time curve from T_0 to subject-specific time to maximum plasma concentration after T_0 .
$AUC_{0-10\text{h}}$	Area under the background-corrected plasma nicotine concentration-time curve from T_0 to 10 hours.
$AUC_{0-\text{last}}$	Area under the background-corrected plasma nicotine concentration-time curve from T_0 to the time of last quantifiable concentration.
$AUC_{0-\infty}$	Area under the background-corrected plasma nicotine concentration-time curve extrapolated from T_0 to infinity.
$\max(C_t/t)_{t \in [0, T_{\max}]}$	Maximum rate of absorption expressed as the maximum of the ratio of background-corrected concentration at a specific time over this time, from T_0 (exclusive) to T_{\max} (inclusive).

All AUC parameters will be calculated using linear trapezoidal with linear interpolation method.

For calculation of λ_z from observed data (to be used for background correction), concentrations BLQ will be set to 0 for pre-administration and prior to the first measurable concentration, and set to missing after the last quantifiable concentration (if applicable).

The following steps will be applied for the other PK parameters:

- Concentrations below the lower limit of quantitation (BLQ) will be set to $\frac{1}{2}$ the lower limit of quantitation (LLOQ) except for any BLQ values after the last quantifiable concentration which will be set to missing.
- The formula for background correction will be applied.
- After the calculation, pre-product administration values will be assigned a value of zero in the analyses. All other values obtained will be reported as is even if these values are BLQ, except for any negative values, which will be set to zero.

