The PK of plasma nicotine presents a biphasic profile, with a typical rapid initial disposition half-life ($t_{1/2a}$) of 1.35 hours, followed by a slower terminal elimination half-life ($t_{1/2z}$) of hours [15]. To ensure a complete nicotine washout between each product use, 3 days without product use (cigarette or P4M3 Gen 2.0) would have been required ($\sim 5 \times$ terminal elimination $t_{1/2z}$). Based on nicotine population PK modeling, it was estimated that nicotine enters in the terminal elimination phase with concentrations decreasing with a terminal elimination rate constant (λ_z) 8 to 10 hours post administration. As a consequence, a minimum of 12 hours has been established in this study design prior to T_0 on Day 1 and approximately 24 hours prior to T_0 on Day 2 and Day 3. Background-concentration correction will be applied to adjust for carry-over effects with adjustment of baseline values to the estimated $t_{1/2z}$ (or λ_z) which will be derived from additional blood sampling on Day 2 and Day 3 for each subject.

The use of estrogen contraceptive is known to accelerate nicotine clearance by 20% to 30% compared to women who do not take estrogen contraceptive [16]. Therefore, for the purpose of this study, use of hormonal contraception containing estrogens is prohibited. This also applies to hormone replacement therapy.

The activity of CYP2A6 will be measured as this enzyme drives the metabolism of nicotine into cotinine and subsequent metabolites. Nicotine metabolism by CYP2A6 varies between individuals of the same ethnicity/race and across ethnicity/race due to genetic variations. These genetic differences could be associated with reduced/increased nicotine metabolism [14].

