On Day 3, 13 blood samples will be collected for determination of nicotine PK after allocated product use. The sample T14 after T0 on Day 3 will not be collected.

On Day 1 to Day 3, subjective effects of liking and craving will be assessed using a VAS (100 mm going from “strong disliking” to “strong liking” for VAS liking, and from “no craving” to “strong craving” for VAS craving) at the following time points in relation to T₀:

Prior to T₀ (for VAS craving assessment only)

- T-15: within 15 minutes prior to T₀

After T₀: (for VAS craving and VAS liking assessment) with a time window as indicated in brackets

- T1 after 4 minutes (\pm 1 minute)
- T2 after 10 minutes (\pm 1 minute)
- T3 after 15 minutes (\pm 1 minute)
- T4 after 30 minutes (\pm 2 minutes)
- T5 after 1 hour (\pm 5 minutes)
- T6 after 2 hours (\pm 5 minutes)
- T7 after 4 hours (\pm 5 minutes)
- T8 after 10 hours (\pm 5 minutes)

Additional subjective effects will be assessed on Day 1 to Day 3 by the ABOUT-Product experience questionnaire administered within 1 to 2 hours after T₀.

On Day 2, additional blood samples will be taken for determination of the nicotine concentration to evaluate terminal elimination half-life (t_{1/2z}) in relation to T₀ from Day 2 at the following time points with a time window as indicated in brackets:

- T1z after 8 hours (\pm 5 minutes) after T₀ from Day 2
- T2z after 12 hours (\pm 5 minutes) after T₀ from Day 2
- T3z after 16 hours (\pm 10 minutes) after T₀ from Day 2
- T4z after 20 hours (\pm 10 minutes) after T₀ from Day 2

After enrollment at Day -1, the use of any other tobacco and nicotine containing products different from the product assigned for 6 minutes *ad libitum* use on Day 1 to Day 3, will not be allowed. Use of tobacco and nicotine containing products will not be restricted after the subject has been discharged from the investigational site on Day 3.

After discharge at Day 3, the subjects will enter a 3-day Safety Follow-Up Period (FU Period) during which AE/SAEs reported by the subjects will be collected and the follow-up of AEs/SAEs ongoing at discharge will be conducted by the investigational site.

Philip Morris Products S.A.
P4M3 Gen 2.0, P4-PK-04-US

██████████ Statistical Analysis Plan Number CA34617

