6.4 Pharmacokinetic Data Summarization and Presentation

SAS software (version 9.4, Cary, North Carolina) will be used for all data presentation and summarization including statistical analyses, summary tables, graphs, and data listings.

Plasma nicotine concentrations (observed and background-corrected,) λ_z (observed only) and other PK parameters (background corrected only) will be summarized with descriptive statistics including number of subjects (n), number and percent of subjects with missing data (Missing, n (%)), arithmetic mean (Mean), standard deviation (SD), percent CV (CV%), standard error of the mean (SEM), 95% confidence interval (95%CI), minimum, first quartile (Q1), median, third quartile (Q3), and maximum. Summaries will be further stratified by Sex.

In addition, geometric mean (Geo. Mean), 95% geometric confidence interval (Geo. 95% CI) and geometric CV (Geo. CV%) will be presented as well, as applicable.

For observed plasma nicotine concentrations, the number and percent of values below LLOQ (BLQ, n(%)) or above ULOQ (ALQ, n(%)) will be presented in each summary table.

Categorical variables will be summarized by frequency statistics (number and percentage).

For endpoints relating to sampling times (e.g., T_{max}) only median, Q1, Q3, minimum and maximum will be presented.

All analyses and summaries will be performed by product and overall.

The analytical data will be presented in the tables/listings to the same precision as received from the analytical laboratory.

The level of precision and rounding for the summary statistics listed in [Section 14.1.5](#).

Where individual data points are missing because of dropouts or other reasons, the data will be summarized based on reduced denominators. Missing PK data will be treated as missing and no data imputation will be conducted.

Mean and individual plasma nicotine concentrations will be presented graphically (linear and semi-log plots; linear plots will be presented with and without SD).

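### SAP 6.3 does not say which terminal rate extrapolates AUC0-infinity, and Days 1 and 3 have too few terminal samples to supply their own

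*SAP*

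**What the plan says.** AUC0-infinity is listed among the main endpoints for Day 1 to Day 3 (Protocol 3.1, SAP 2). It enters the main ANOVA (SAP 6.5.1) and the liking ANCOVA (programmer note to SAP Table 15.2.2.2.4). Its definition in SAP 6.3 is the area under the background-corrected "curve extrapolated from T_0 to infinity". Protocol 12.5.1 leaves further derivation detail to the SAP.

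On the rate, SAP 6.3 says that λz "will be estimated from the Day 2 PK samples listed in" SAP 6.1, and continues: "The regression analysis should contain data from at least 3 different time points in the terminal phase". A later sentence on values below quantification refers to λz calculated "from observed data (to be used for background correction"). The remaining parameters come from an NCA of the corrected concentrations. SAP 6.4 summarises λz from observed data only and the other parameters from corrected data only. The one λz listing (15.3.3.1.10) is labelled Day 2.

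On sampling, Protocol 4.2 places the start of the terminal phase at "8 to 10 hours post administration". The extra samples at 8, 12, 16 and 20 h follow Day 2 use only. For Day 3, "The sample T14 after T0 on Day 3 will not be collected", so its last sample is at 10 h.

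**The concern.** Extrapolation to infinity divides the last concentration by a terminal rate. The SAP gives a rate, ties it in words to another purpose, and then moves to per-profile NCA without naming a rate for the extrapolation. Two analysts could follow the text and produce different AUC0-infinity values.

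The gap matters because the days are not sampled alike. Only Day 2 can support a terminal fit of three or more points. If the NCA software chooses a rate for each corrected profile, the Day 3 rate must come mostly from samples taken before the terminal phase. That rate is too steep and the extrapolated area too small. The planned outputs would not reveal this: no λz from corrected profiles is summarised, and the percentage extrapolated is not among the parameters.

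**Working it through.** **Sampling schedule.** The stated counts are 15 (Day 1), 14 (Day 2), 13 (Day 3) and 4 half-life samples: 15 + 14 + 13 + 4 = 46. At 5.0 mL each this is 230 mL, which agrees with Protocol 7.7.1.

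**Terminal-phase samples, counted from 8 to 10 h.**

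| Day | Times | Count |
|---|---|---|
| 1 | 10, 24 h | 2 |
| 2 | 8, 10, 12, 16, 20, 24 h | 6 (5 if counted from 10 h) |
| 3 | 10 h | 1 |

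A three-point fit that includes the last sample can start no later than 4 h on Day 1 (4, 10, 24 h) and no later than 2 h on Day 3 (2, 4, 10 h).

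**Illustration.** The initial half-life of 1.35 h is from Protocol 4.2. The terminal value is missing from the text available; Protocol 4.2 equates 3 days with about five terminal half-lives, so 72/5 = 14.4 h is inferred. The fast-phase share A of 0.80 to 0.95 is an assumption, as is a terminal range of 10 to 18 h. The curve starts at its peak at time zero, and every sample is taken as quantifiable.

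C(t) = A·exp(−0.5134t) + (1 − A)·exp(−0.04814t)

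True AUC0-infinity = A/0.5134 + (1 − A)/0.04814

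Estimate = linear-trapezoid AUC0-last + C_last/λz

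Worked case, A = 0.90:
- True area: 0.9/0.5134 + 0.1/0.04814 = 1.753 + 2.077 = 3.830.
- C(2) = 0.4131, C(4) = 0.1979, C(10) = 0.0671. The log-linear slope through these is 0.2164 per h, a half-life of 3.2 h.
- The trapezoid area to 10 h at nominal times is 2.733.
- Own-profile rate: 2.733 + 0.0671/0.2164 = 3.043; 3.043/3.830 = 0.79.
- Day 2 rate, fitted to 8 through 24 h (0.0580 per h, half-life 12.0 h): 2.733 + 0.0671/0.0580 = 3.890; 3.890/3.830 = 1.02.

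Results at 14.4 h, as estimate divided by true:

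| A | Day 3, own fit | Day 3, Day 2 rate | Day 1, own fit |
|---|---|---|---|
| 0.80 | 0.73 | 1.01 | 0.98 |
| 0.90 | 0.79 | 1.02 | 0.99 |
| 0.95 | 0.89 | 1.03 | 1.02 |

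Own-profile Day 3 half-lives are 4.5, 3.2 and 2.4 h. If the Day 2 fit starts at 10 h instead of 8 h, the Day 2 rate column becomes 1.02, 1.04 and 1.06. For terminal half-lives of 10 to 18 h, the Day 3 own-fit ratio runs from 0.65 to 0.98 and the Day 1 own-fit ratio from 0.93 to 1.07. The share of the true area beyond 10 h is 23 to 45% at 14.4 h, which is why the choice of rate matters.

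**Effect on summaries.** All six sequences are used, so each product falls on Day 3 in 2 of 6, that is 12 of 36 subjects. A common Day 3 factor k, with no bias on the other days, multiplies each product's geometric mean by k^(1/3): 0.73^(1/3) = 0.90 and 0.89^(1/3) = 0.96. Geometric means would be about 4 to 10% low, and the spread wider. On the log scale the same k is a constant added to period 3, which the period term absorbs.

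**The case against.** The strongest reply is that the SAP already points to one rate per subject. It estimates λz once, on Day 2, applies that rate to every day in the background correction, and plans no λz listing for Day 1 or Day 3. Carrying the same rate into the extrapolation is a natural reading, and nothing forbids it. This stands, but the SAP does not say so. Per-profile NCA is an equally ordinary reading of the text, and Listing 15.3.3.1.10 adds doubt: its shell has columns for all three products for each subject, although each subject uses only one product on Day 2.

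A reader might go further and infer that AUC0-infinity cannot be derived on Days 1 and 3, leaving 72 of 108 planned product-days without a value and no within-subject ratio. The documents do not support that. The three-point rule is written for the Day 2 regression, and the reference to background correction sits in a sentence about values below quantification and does not say only.

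A reader might also expect a clear downward bias on Day 1. With exact integration the own-profile Day 1 estimate is 6 to 7% low at 14.4 h. The SAP specifies linear trapezoids, which overstate a convex decline over the long late intervals, and this largely cancels it.

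Finally, the sequences are balanced, both the ANOVA and the liking ANCOVA include period, the study tests no hypothesis, and AUC0-10h is available on every day. All of this stands and limits the harm to the product comparisons.

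**Conclusion.** The point holds as an unspecified extrapolation rate for a main endpoint, with a material consequence under one ordinary reading of the text. The sample counts come straight from the documents. The bias depends on the assumed curve: about 11 to 27% low on Day 3 at a terminal half-life of 14.4 h, about 2 to 35% low over 10 to 18 h, and little on Day 1. With the Day 2 rate, Day 3 is within a few percent at 14.4 h. Most of the average effect drops out of the product ratios and the liking ANCOVA. What remains is in the reported geometric means and CVs, and in bias that varies between subjects with their half-life and fast-phase share. It should be settled before the analysis is run, but the documents do not show that the endpoint is underivable or that the ratios are invalid.

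**What to change.** State in SAP 6.3 that on all three days AUC0-infinity = AUC0-last + C_last/λz, where C_last is the last quantifiable concentration after background correction and λz is the same subject's Day 2 estimate. Switch off per-profile λz selection in the NCA software, and add the percentage extrapolated to the parameter listings.

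The cost is one sentence, one software setting and one listed variable; no sampling changes. The downside is that one rate per subject is assumed common to the three products. The background correction already makes that assumption.
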